5.7. Handling of Missing Data

5.7.1. Start Dates for Adverse Events

A treatment emergent adverse event (TEAE) is an adverse event not present prior to the initiation of study drug dosing or is an already present event that worsens either in intensity or frequency following the initiation of study drug dosing.

Investigators will be asked to respond "Yes" or "No" on the CRF as to whether the AE started after the subject took the first dose of study treatment. An AE with a response of "Yes" and with an onset date on or before 10 days after the last dose of study treatment will be classified as a TEAE. If the investigator's response is missing, then the treatment emergent status will be derived based on the AE onset date and time relative to the date and time of the subject's first dose of study treatment, as follows: if the AE onset date and time are unknown, it will be assumed that the AE is a TEAE; if the AE onset time is unknown but the AE onset date is the same date as the first dose of study treatment, it will be assumed that the AE is a TEAE. Adverse events that occur more than 10 days after the last dose will not be considered treatment emergent and will be tabulated by treatment group separately.

Missing and incomplete ("partial") dates for AEs will be imputed for the purpose of estimating the time of the event or medication usage in relationship to study treatment. Any data listings will display the original dates as reported in the database.

Neurocrine Biosciences, Inc. Statistical Analysis Plan Study NBI-1065846-MDD2020 16August2023

The missing and incomplete ("partial") dates for AEs will be imputed using the following algorithm for start dates:

- missing day: if the same month and year as the first dose of randomized study treatment, impute the first dose date of randomized study treatment; otherwise impute the 1st of the month.
- missing day and month: if the same year as the first dose of randomized study treatment, impute the first dose date of randomized study treatment; otherwise impute 1st January.

There will be no imputation for AE stop dates.

If any of the above imputations result in a start date that is later than an existing (not imputed) stop date for the event, the start date will be imputed as the stop date.

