10. ADVERSE EVENTS

All AEs, whether observed by the investigator, reported by the subject, noted from laboratory findings, or identified by other means, will be recorded from the time the subject has signed the ICF until the subject's final study visit/contact (or upon ET).

10.1. **Definition**

An AE is any untoward medical occurrence in a patient or clinical investigation subject administered a pharmaceutical product that occurs after enrollment into the study and which does not necessarily have a causal relationship with the study treatment. An AE can therefore be any unfavorable and unintended sign (including an abnormal laboratory finding, for example), symptom, or disease temporally associated with the use of a medicinal product, whether or not considered related to the medicinal product.

AEs include, but are not limited to, any of the following:

- Worsening or change in nature, severity, or frequency of conditions present at the start of the study
- Subject deterioration beyond what would be expected due to the primary illness
- Intercurrent illness
- Drug interaction

C-SSRS suicidal ideation type 4, C-SSRS suicidal ideation type 5, and all reports of suicidal behavior and clinically significant suicidal ideation must be documented as AE or SAE (if SAE criterion is met). C-SSRS suicidal ideation types 1, 2, or 3 must be documented as AEs or SAEs (if SAE criterion is met) if considered clinically significant by the investigator.

Subjects should be questioned in a general way, without asking about the occurrence of any specific symptom. The investigator should attempt to establish a diagnosis of the event based on signs, symptoms, and/or other clinical information. In such cases, the diagnosis should be documented as the AE and not the individual signs/symptoms. Following questioning and evaluation, all AEs, whether believed by the investigator to be related or unrelated to the study treatment, must be documented in the subject's medical records, in accordance with the investigator's normal clinical practice and on the AE eCRF. Each AE is to be evaluated for duration, intensity, frequency, seriousness, outcome, other actions taken, and relationship to the study treatment.

The following are not considered AEs:

- Continuous persistent disease/symptom present before study treatment administration, unless it unexpectedly progresses, or increases in severity following study treatment administration
- Study treatment failure or lack of efficacy

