9.3. Adverse Events

Adverse events are recorded in the eCRF. Each AE will be coded to SOC and PT using MedDRA.

A treatment-emergent adverse event (TEAE) is an AE that occurs after the initiation of randomized study treatment dosing. Investigators will be asked to respond "Yes" or "No" on the eCRF as to whether the AE started after the subject took the first dose of study drug. An AE with a response of "Yes" will be classified as a TEAE. If the investigator's response is missing, then the treatment emergent status will be derived based on the AE onset date and time relative to the date and time of the subject's first dose of study drug. If the AE onset date and time are unknown, it will be assumed that the AE is a TEAE. If the AE onset time is unknown but the AE onset date is the same date as the first dose of study drug, it will be assumed that the AE is a TEAE.

The frequency tables will include the number and percentage of unique subjects experiencing each event at least once during the study. Unless otherwise specified, summary tables will include events with a start date on or after the date of the first dose of randomized study treatment and up to the last dose of study treatment + 10 days.

Two versions of the primary TEAE frequency tables will be presented by treatment group:

- Frequency of TEAEs by SOC and PT, with SOCs sorted alphabetically and PTs within each SOC sorted by decreasing frequency (number of unique subjects) in the active treatment group.
- Frequency of TEAEs by PT, with PT sorted by decreasing frequency (number of unique subjects) in the active treatment group.

Summary tables of severe TEAEs will be presented by treatment group. The number and percentage of subjects with a severe TEAE will be presented by PT within SOC (presented in the same method as the primary TEAE table). The first line of the table will display the number and percentage of subjects with at least one severe TEAE.

An AE overview summary table will be provided which summarizes the number and percentage of subjects with any TEAE, any TEAE leading to study treatment discontinuation, any serious TEAE, and any TEAE leading to death. The summary table will also include the maximum TEAE severity (mild, moderate, severe) reported for each subject.

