In addition, tables will be provided for non-treatment emergent AEs (AE start dates after last dose date +10 days) separately. These tables will be summarized by treatment group and presented by PT within SOC, with SOCs sorted alphabetically and PTs within each SOC sorted by decreasing frequency (number of unique subjects) in the active group.

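### The SAP defines TEAEs to include worsening of an existing event, but no classification step uses worsening, so an AE recorded before dosing that worsens on treatment can be left out of the TEAE outputs

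*SAP*

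**What the plan says.** SAP 5.7.1 (Start Dates for Adverse Events) opens with a two-part definition. A TEAE is an event that was not present before dosing, "or is an already present event that worsens either in intensity or frequency following the initiation of study drug dosing".

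The next paragraph of 5.7.1 gives the rule that assigns the flag. The investigator answers a Yes/No question on the CRF "as to whether the AE started after the subject took the first dose of study treatment". A TEAE is then "An AE with a response of 'Yes' and with an onset date on or before 10 days after the last dose of study treatment". If the answer is missing, "treatment emergent status will be derived based on the AE onset date and time relative to the date and time" of first dose. Two defaults apply in that case: unknown onset, or onset on the day of first dose at an unknown time, is taken as treatment-emergent.

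SAP 9.3 (Adverse Events) gives a second definition: "A treatment-emergent adverse event (TEAE) is an AE that occurs after the initiation of randomized study treatment dosing". It repeats the Yes/No question and the fallback. It also says that, unless otherwise specified, "summary tables will include events with a start date on or after the date of the first dose of randomized study treatment", up to 10 days after the last dose. For the remaining events, "tables will be provided for non-treatment emergent AEs (AE start dates after last dose date +10 days) separately".

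Protocol 11.5.2 defines TEAEs by onset date alone. Protocol 10 collects AEs from signature of the consent form. Protocol 10.1 lists as an AE "Worsening or change in nature, severity, or frequency of conditions present at the start of the study". Protocol 10.2 gives each AE of a randomized subject its own eCRF entry.

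**The concern.** The worsening limb in SAP 5.7.1 is stated but never put into effect. No step looks at a change in intensity or frequency, and no step turns a No answer into a TEAE. A programmer cannot satisfy both the definition and the rule when an AE began during screening, continued past first dose and then got worse on a single record.

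Such records can exist. AEs are collected from consent, and screening lasts up to 28 days with a possible 14-day extension (Protocol 4.1). An on-treatment increase in intensity is information the safety tables are meant to show. Protocol 8.1 makes discontinuation mandatory when an AE becomes intolerable, including through its frequency or severity. A pre-dose AE could meet that criterion on treatment, appear in disposition as a discontinuation for an AE, and be absent from both the table and the listing of TEAEs leading to discontinuation (SAP 9.3.1). With approximately 20 centers, whether a case counts could turn on how a site keeps its records.

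**Working it through.** The plan states no figure on this point. The check is a trace of cases through the SAP 5.7.1 rule and the SAP 9.3 table rules. In each case the AE has its onset after consent and before first dose, and it worsens after first dose, unless stated otherwise.

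| Case | 5.7.1 definition | 5.7.1 / 9.3 rule | Output |
|---|---|---|---|
| (a) One record, intensity updated, answer No | TEAE | Not a TEAE | Start date precedes first dose, so outside the 9.3 TEAE tables. It does not fall more than 10 days after last dose, so outside the non-treatment-emergent tables too |
| (b) One record, answer missing, pre-dose onset known | TEAE | Onset derivation gives not a TEAE | As (a) |
| (c) Worsening entered as a new record with post-dose onset, answer Yes | TEAE | TEAE | Counted |
| (d) Answer missing and onset unknown, or onset on the day of first dose at unknown time | Depends on the true onset and course | TEAE by default | Classed as a TEAE |

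Cases (a) and (b) are where definition and rule disagree. In both, the event appears in no planned AE frequency table. It is therefore also absent from the severe-TEAE table, the maximum-severity line of the overview table and the outputs for TEAEs leading to discontinuation, all of which are restricted to TEAEs.

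Which of (a) and (c) occurs depends on data entry. Protocol 10.1 makes worsening an AE, and Protocol 10.2 gives each AE an entry. Protocol 10.2 lists dates of onset and resolution, intensity and frequency among the items recorded. It lists no date of worsening, and it does not say that an AE already on file gets a second entry when it worsens.

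The gap is confined to AEs already on record before first dose. A condition held only as medical history has no AE record to update, so its worsening would be entered as a first AE record with post-dose onset, as in case (c).

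Scale: 88 subjects randomized 1:1 gives 88 / 2 = 44 per arm, and 1 / 44 = 2.3%. One subject moved in or out of a table changes an arm's incidence by 2.3 percentage points. Neither document gives a rate of pre-dose AEs, a rate of worsening, or the share of sites that would update an old record, so no expected count follows.

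**The case against.** The strongest reply is that the protocol already settles the matter. Protocol 10.1 excludes from AEs a persistent condition present before treatment unless it progresses unexpectedly or becomes more severe after treatment. It separately lists worsening as an AE, and Protocol 10.2 requires one entry per AE. Read together, post-dose worsening is its own AE with its own post-dose start, the answer is Yes, and the onset-based rules agree with the worsening limb. The eCRF completion instructions, which Protocol 13 says are covered at site orientation, may say so outright, and they are not among the documents reviewed.

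Much of this stands. It shows that the loss is conditional, and it is a sensible reading of the protocol. It is still an inference: neither document expressly tells a site to open a new record or give a new onset date when an AE already on file worsens.

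Three stronger readings are tempting and are not supported.

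- That the rule counts only events that started after first dose. The two defaults for a missing answer (case d) go beyond that.
- That a count of lost cases can be given. If one assumed that 10% to 30% of subjects have a pre-dose AE and 10% to 20% of those worsen, the product would run from 88 x 0.10 x 0.10 = 0.9 to 88 x 0.30 x 0.20 = 5.3 subjects over both arms. Those rates are assumptions, and the product supposes that every such case is kept on the old record. It is at most an upper bound under those rates.
- That the worsening would be invisible. The SAE listing in SAP 9.3.2 is not limited to TEAEs. Disposition reasons are tabulated regardless of TEAE status (SAP 6.1). Laboratory, ECG and C-SSRS changes are summarized from measured values (SAP 9.4, 9.7, 9.8.1). Some cases would still show there.

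**Conclusion.** The concern holds as an internal inconsistency with a conditional consequence. The SAP's definition includes worsening. Its classification and table rules do not, and neither do SAP 9.3's own definition and Protocol 11.5.2. Where a site opens a new record, nothing is lost. Where it updates an existing pre-dose record, an event that the SAP defines as treatment-emergent drops out of the TEAE-based outputs and is not picked up by the non-treatment-emergent tables.

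The number of subjects affected cannot be computed from the documents. The conclusion rests on the absence of an express data-entry instruction in the protocol and SAP; if the eCRF instructions contain one, only the wording needs alignment. Safety analysis is descriptive, so no hypothesis test is affected. The point should be corrected because AE tables in arms of 44 are sensitive to single subjects and the correction is cheap.

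**What to change.** 1. Use one TEAE definition, with the worsening limb, in SAP 5.7.1, SAP 9.3 and Protocol 11.5.2. (The protocol and SAP also differ on how long after last dose an event stays treatment-emergent. That is a separate matter, which this wording does not settle.)
2. State that a post-dose increase in intensity or frequency of an ongoing pre-dose AE is entered as a new AE record with the date of worsening as its onset. The existing Yes/No and start-date rules then count it without change. Putting a date-of-worsening rule in the SAP alone would not work, because a single updated record carries no such date.
3. Before database lock, check AE records with pre-dose onset for changes in intensity or frequency made after first dose. The EDC audit trail keeps these (Protocol 12.1). Query the site for the date of worsening, since the audit trail dates the edit and not the event, and classify confirmed cases as TEAEs.

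Cost: wording in two SAP sections, one sentence in Protocol 11.5.2, one line of eCRF completion guidance if it is not already there, and one data check with queries limited to the records it finds. Protocol 12.7 requires a formal amendment for any protocol change. If none is otherwise planned, the SAP can state that its definition departs from Protocol 11.5.2 and why. No new assessment or eCRF field is needed.

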11.5.2. Safety Analyses

Safety data from this study will be analyzed using the safety analysis set. The subject incidence of TEAEs will be tabulated by treatment group for AEs, SAEs, fatal AEs, and AEs leading to discontinuation of study treatment. TEAEs are those AEs with onset dates on or after the date of the first dose of study treatment and on or before 55 days after the date of the last dose of study treatment. Descriptive statistics by treatment group will be generated for additional safety data, including selected laboratory analytes, vital signs, ECG parameters, C-SSRS, which will be further described in the SAP.

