9.3.2. Deaths and Other Serious Adverse Events

Summary tables of Treatment-emergent SAEs and deaths will be presented by treatment group. The tables will include the frequency of SAEs presented by PT within SOC (presented in the same method as the primary TEAE table).

Separate listings of SAEs and fatal TEAEs will also be provided. Each listing will include subject ID, treatment group, last treatment received prior to the onset time of the SAE or fatal TEAE, study day of the SAE or fatal TEAE, and any additional relevant information from the AE eCRE.

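### The SAP closes the TEAE window 10 days after the last dose where the protocol sets 55, so events in most of the safety follow-up leave the TEAE, SAE and death tables

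*SAP*

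**What the plan says.** Protocol Section 11.5.2 defines TEAEs as events with onset from the date of the first dose and "on or before 55 days after the date of the last dose of study treatment". It tabulates TEAE incidence by treatment group for AEs, SAEs, fatal AEs and AEs leading to discontinuation of study treatment. Protocol Section 11.4.4 and SAP Section 4.4 both list the occurrence of TEAEs as a safety endpoint.

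The SAP uses a different window:

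- **Section 5.7.1** says that an event marked as starting after the first dose and "with an onset date on or before 10 days after the last dose of study treatment will be classified as a TEAE". It then states: "Adverse events that occur more than 10 days after the last dose will not be considered treatment emergent and will be tabulated by treatment group", in tables apart from the TEAEs.
- **Section 9.3** classifies every event with a Yes response to the same question as a TEAE and gives no upper time limit. It then limits the summary tables, unless otherwise specified, to events from the first dose "up to the last dose of study treatment + 10 days". It adds that "tables will be provided for non-treatment emergent AEs (AE start dates after last dose date +10 days) separately".
- **Section 9.3.2** says: "Summary tables of Treatment-emergent SAEs and deaths will be presented by treatment group". It also says: "Separate listings of SAEs and fatal TEAEs will also be provided". The SAE listing has no stated window. The fatal listing is limited to TEAEs.

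**The concern.** The two documents define the same named endpoint differently. Protocol Section 11 describes the SAP as adding detail to the methods summarized there, yet the SAP replaces the window without giving a reason or recording a departure.

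The 55-day figure is not isolated in the protocol. The contraception requirement (Sections 5.1 and 10.6) uses the same 55 days, safety visits are scheduled 4 and 8 weeks after the last dose, and Section 10 collects adverse events to the final visit.

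An event with onset between 11 and 55 days after the last dose would be absent from the main TEAE, severe TEAE, serious TEAE and death tables. Reported incidence can then only be equal to or lower than under the protocol definition.

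The cut also sits badly with the SAP's other safety outputs. Laboratory data are summarized through Day 106 (Section 9.4), and the C-SSRS summary covers all postbaseline assessments (Section 9.8.1). Protocol Section 9.3.6 requires type 4 or 5 ideation to be recorded as an AE. Such an event with onset on Day 78 would appear in the C-SSRS summary but not in the TEAE tables.

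**Working it through.** Neither document states the length of the resulting windows, so there is no figure of the plan's own to reproduce. The day counts follow from these inputs.

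**Inputs**
- Scheduled last dose, L: Day 50 (Protocol Section 6.2).
- Protocol TEAE window: Day 1 to L + 55 (Protocol Section 11.5.2).
- SAP TEAE window: Day 1 to L + 10 (SAP Sections 5.7.1 and 9.3).
- Safety follow-up: Days 58 to 106 (Protocol Section 9.6.3), which is 106 − 58 + 1 = 49 days, with visits on Days 78 and 106.

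**Subject dosed on schedule (L = 50)**
- Protocol window ends on Day 50 + 55 = 105.
- SAP window ends on Day 50 + 10 = 60.
- Days relabelled: 105 − 60 = 45 (Days 61 to 105).
- Share of protocol-defined treatment-emergent time: 45/105 = 42.9%.
- Share of the protocol's post-dose window: 45/55 = 81.8%.
- Follow-up days inside the SAP window: Days 58, 59 and 60, so 3 of 49. Outside: 46/49 = 93.9%.
- Of those 46 days, 45 are inside the protocol window. Day 106 is outside both.

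**Sensitivity to the ±2-day dosing window**

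| Last dose | SAP window ends | Follow-up days inside | Follow-up days outside |
|---|---|---|---|
| Day 48 | Day 58 | 1 of 49 | 48/49 = 98.0% |
| Day 50 | Day 60 | 3 of 49 | 46/49 = 93.9% |
| Day 52 | Day 62 | 5 of 49 | 44/49 = 89.8% |

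**The two follow-up visits.** Day 78 is L + 28, which is inside the protocol window and outside the SAP window. Day 106 is L + 56, one day past the protocol window as well. Classification goes by onset date, not by the visit at which the event is reported. An event reported on Day 106 with onset between Days 61 and 105 is a TEAE under the protocol and not under the SAP.

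**Subject who stops early but stays in the study** (Protocol Section 8.1). If the Day 8 dose is the last, the SAP window closes on Day 8 + 10 = 18 and the protocol window on Day 8 + 55 = 63. Days 19 to 57 are 57 − 18 = 39 of the 57 days of the nominal Treatment Period, and all of them become non-treatment-emergent.

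**Serious and fatal events.** Take a death on Day 70 with L = 50, which is L + 20, from an event that also began after Day 60. Under the protocol it belongs in the fatal TEAE table. Under the SAP it is missing from the overview table, the death table and the fatal listing. It can appear in the SAE listing and in the separate late-event table, for which only a breakdown by preferred term within system organ class is specified.

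**The case against.** The strongest reply is that nothing is lost. Later events are tabulated by treatment group in their own tables, and the SAE listing is not limited to treatment-emergent events, so a late death can still be found there. That is correct, and it narrows the gap: the loss is from the main tables and from any serious, severe or fatal summary of late events.

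Other points also stand:

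- The 43% is calendar time. The documents give no AE rate by period, so the number of reclassified events is unknown and may be small.
- The cut-off is the same in both arms, safety is descriptive, and no efficacy result is touched. TEAEs leading to discontinuation should change little, since they normally begin before or near the last dose.
- Section 9.3 lacks an upper limit in its definition but filters its tables to 10 days, so that inconsistency mainly affects event flags and listings.
- A separate late window could be defended. The medication prohibitions and the stable-antidepressant rule end at Day 57 or early termination, so later events may reflect new medication. The documents also give no half-life from which to judge how long exposure lasts. The SAP does not make this argument.

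None of this removes the contradiction. A separate table labelled non-treatment-emergent does not report the incidence that the protocol defines as TEAE.

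**Conclusion.** The concern holds and should be corrected before database lock and unblinding. The SAP's 10-day window contradicts the protocol's 55-day window on a named safety endpoint, without a stated reason. For a last dose on Day 50, 45 of 105 days (43%) of protocol-defined treatment-emergent time is relabelled, and 94% of follow-up days lie outside the SAP window (90% to 98% across the dosing window). A subject who stops early can have most of the nominal Treatment Period relabelled.

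These sizes rest on the scheduled dosing days and measure time at risk, not events. How far the reported counts would change cannot be determined from the documents. The SAP also needs one TEAE definition in place of the two in Sections 5.7.1 and 9.3.

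**What to change.** Use the protocol's definition, onset from the first dose to 55 days after the last dose, once and in the same words in SAP Sections 5.7.1 and 9.3. Move the start of the separate non-treatment-emergent tables to match. Those tables will then be nearly empty, since the last visit is nominally 56 days after the last dose. That follows from the protocol's definition.

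If the 10-day split is wanted, present it as an additional on-treatment summary with its purpose stated. It would also help to state that the SAE listing and a listing of all deaths cover the whole collection period, so that no serious or fatal event depends on the window.

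The cost is SAP wording and a changed cut-off in the AE programs. No new data are needed. Reported TEAE counts may be slightly higher.
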